### 14.0 BIOSTATISTICS

The purpose of this study is to assess the efficacy of Everolimus in patients with progressive urothelial cancer who have received prior cytotoxic chemotherapy. Historically, patients in this setting experience a median time to progression of 2-3 months (as illustrated in Section 3.1). Thus, the primary endpoint of this study will be the proportion of patients who are progression-free after two months on-study.

The sample size and stopping rules will be determined according to Simon's Minimax two-stage design. A two-month progression free survival rate of 50% would be considered not promising, while a 70% two-month PFS rate would be considered promising. In Stage 1 of the trial, 23 evaluable patients will be accrued to the study. If twelve or more patients demonstrate progression on imaging after two months on-study, the study will be terminated early and declared to have a negative result. If 13 or more patients are progression-free at two months, enrollment will be extended to accrue a total of 37 patients. If 24 or more patients are progression-free after their two-month scan (i.e. after Stage 2), the treatment will be declared effective and worthy of further testing.

**Patients will be considered inevaluable for the primary objective (PFS at 2 months) if they receive ≤one cycle of protocol therapy and are discontinued from protocol treatment for either rapid clinical deterioration related to progression of disease or adverse events unrelated to Everolimus. Patients with still be evaluable for toxicity assessment.**

For the purposes of this study, the Type I (false acceptance of a non-promising therapy) and Type II (false rejection of a promising therapy) error rates have been set at 0.05 and 0.20, respectively. This statistical design would effectively discriminate between two-month PFS rates of <50% and >70% and yields 80% probability of a positive result if the true two-month PFS rate is >70%. It yields 95% probability of a negative result if the true two-month PFS rate is <50%. The probability of early stopping under the null hypothesis is 66%.

The secondary endpoint of response rate will be estimated as the proportion of patients meeting the criteria outlined in Section 3.4.2.3 for a complete response or partial response. This proportion will be reported along with its binomial confidence interval.

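### Section 14.0 sizes Stage 1 in evaluable patients and the final stage in patients, so the stated 5% and 80% error properties have no defined denominator

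*Combined protocol and SAP*

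**What the plan says.** All the relevant text is in Section 14.0 (Biostatistics) of the combined protocol and SAP.

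- Design: "The sample size and stopping rules will be determined according to Simon's Minimax two-stage design".
- Rates: "A two-month progression free survival rate of 50% would be considered not promising", while "a 70% two-month PFS rate would be considered promising". The section does not say whether these rates describe all treated patients or evaluable patients only.
- Stage 1: "In Stage 1 of the trial, 23 evaluable patients will be accrued to the study". The trial continues if at least 13 are progression-free.
- Final stage: "enrollment will be extended to accrue a total of 37 patients". The word *evaluable* is absent. The treatment is declared effective if at least 24 are progression-free, a fixed count with no stated denominator.
- Evaluability: "Patients will be considered inevaluable for the primary objective (PFS at 2 months) if they receive" no more than one cycle and stop for rapid deterioration from progression or for adverse events unrelated to everolimus. They stay evaluable for toxicity.
- Operating characteristics: the "error rates have been set at 0.05 and 0.20, respectively", and the design "yields 80% probability of a positive result if the true two-month PFS rate is >70" percent. Early stopping under the null is given as 66%.

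No section says that inevaluable patients are replaced, that 37 means evaluable patients, or what happens to the cut-off of 24 if fewer than 37 are evaluable.

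**The concern.** A two-stage binomial rule is calibrated to fixed denominators. Here the first denominator is in one unit, the second is in another or is silent, and the section also defines patients who fall between the two. The go/no-go decision then depends on a choice the plan has not made.

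Two different errors are at stake. If accrual closes at 37 enrolled and some are inevaluable, fewer patients can contribute to an unchanged target of 24, and an active drug is more easily missed. If enrolment continues until 37 are evaluable, the patients dropped and replaced include those who deteriorated quickly from progression. Section 12.4.5 counts progression and death as PFS failures, so removing such patients raises the observed rate without any change in the drug.

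**Working it through.** **Inputs (Section 14.0).** Stage 1 n = 23, continue at 13 or more; final n = 37, success at 24 or more; p0 = 0.50, p1 = 0.70. Continuing at 13 is used because stopping at 12 or fewer is what gives the stated 66%.

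**Formula.** With n patients counted at the end and true rate p:

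P(positive) = Σ (x = 13 to 23) C(23,x) p^x (1−p)^(23−x) × P[Bin(n−23, p) ≥ 24−x]

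**Step 1: reproduce the plan (n = 37).**
- p = 0.50: P(positive) = 0.048 (stated 0.05).
- p = 0.70: P(positive) = 0.801 (stated 80%).
- P[Bin(23, 0.50) ≤ 12] = 0.661 (stated 66%).

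The figures are correct for 37 counted patients. Power exceeds 80% by only 0.1 percentage point, so there is no reserve.

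**Step 2: reading A. 37 means enrolled, and 70% is the rate among evaluable patients.** Stage 1 keeps 23 evaluable, the cut-off stays at 24, and k Stage 2 patients are inevaluable, so n = 37 − k. The value of k is assumed.

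| Inevaluable in Stage 2 | Evaluable n | Type I error | Power at 70% |
|---|---|---|---|
| 0 | 37 | 0.048 | 0.801 |
| 1 | 36 | 0.032 | 0.734 |
| 2 | 35 | 0.020 | 0.651 |
| 3 | 34 | 0.012 | 0.555 |
| 4 | 33 | 0.007 | 0.450 |

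Averaged over a binomial number of losses among the 14 Stage 2 patients, an assumed 5%, 10% or 15% chance of being inevaluable gives power of 0.75, 0.69 or 0.63.

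**Step 3: reading B. 37 means evaluable, with replacement.** Let a fraction e of treated patients be excluded, all of them failures (assumption). The rate among evaluable patients is then p(all)/(1 − e). For a drug with a true all-treated rate of 50%:
- e = 3%: 0.50/0.97 = 0.515, and P(positive) at n = 37 is 0.070.
- e = 5%: 0.50/0.95 = 0.526, and P(positive) at n = 37 is 0.090.

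The false-positive rate is therefore about 0.07-0.09 against the stated 0.05.

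**Step 4: all treated patients at both stages.** Each of the 37 treated patients is a success or a failure, so n is always 37. With p defined as the all-treated rate, Step 1 applies unchanged (0.048 and 0.801), whatever the number of early stoppers.

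**The case against.** The strongest reply is that 37 evaluable is plainly meant. Enrolment is extended to a total, the 23 evaluable patients are part of that total, and the stated figures reproduce with 37 in the denominator. That reading is plausible. The accrual sentence does not settle it: at 2-4 patients per month, 37 patients take 37/4 = 9.25 to 37/2 = 18.5 months, which fits an approximate 10-20 months but does not show which unit was meant. Even if the reading is granted, it removes the power problem only by replacing early progressors, which is reading B.

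A second reply is that the power loss needs 70% to be the rate among evaluable patients. This also stands. Suppose 70% is the all-treated rate, excluded patients are all failures, Stage 1 is filled with 23 evaluable patients (rate p/(1 − e)) and 14 more are enrolled (rate p). Power is then 0.85 and 0.88 for e = 3% and 5%, above the stated value. The same mixture at an all-treated rate of 50% gives a false-positive rate of 0.061 and 0.072, so the stated pair still does not hold.

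A third reply is that the error is conservative. That is true of reading A with the cut-off held at 24, but not of reading B.

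A reader might also infer that the plan anticipates inevaluable patients, or that an active drug will in general be rejected far more often than 20% of the time. The documents support neither. They define a narrow category and give no expected number. Under reading A the rejection risk is 27% with one such patient, and the larger figures need three or four.

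**Conclusion.** The concern holds as a problem of mixed units and an undefined target population, not as a demonstrated loss of power. The arithmetic in Section 14.0 is right for exactly 37 counted patients whose rates are the stated 50% and 70%. The text does not secure that condition, and none of the readings examined guarantees both error rates once any patient is inevaluable.

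The size depends on the reading: power 0.73 with one and 0.65 with two inevaluable Stage 2 patients under reading A, or a false-positive rate of about 0.07-0.09 under reading B with 3-5% excluded. Both rest on an assumed number of inevaluable patients. Reading B also assumes that every excluded patient would have failed, which is reasonable for rapid progression and less certain for unrelated adverse events. The point should be corrected because it bears directly on the trial's go/no-go rule.

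**What to change.** Rewrite the rule in Section 14.0 with one unit throughout:

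- Define both 23 and 37 as all patients who receive everolimus.
- Count any patient not shown to be progression-free at the two-month scan as a failure, including those who stop early for any reason.
- Keep 13 of 23 and 24 of 37.
- State that the 50% and 70% rates refer to all treated patients.
- If wanted, report the evaluable-only result as a sensitivity analysis that does not drive the decision.

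Inserting *evaluable* before the final patient count is not enough, because it leads to reading B.

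The cost is one or two sentences and no extra patients. The 5% and 80% then hold as stated. Patients who stop early for unrelated adverse events will count as failures, so the estimated rate is slightly less favourable. The change does not raise power for a drug whose rate is 70% among evaluable patients only: with one inevaluable Stage 2 patient that remains 0.73. What it does is make the stated power true for a population the plan has defined.

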## Memorial Sloan-Kettering Cancer Center IRB Protocol

IRB#: 08-123 A(8)

Footnotes for Schedule of Events	
1. Complete blood count (CBC) with differential and platelets	
2. Comprehensive panel (i.e. serum electrolytes including sodium, potassium, chloride, bicarbonate, phosphorus, calcium, glucose, blood urea nitrogen, creatinine, SGOT (AST), SGPT (ALT), alkaline phosphatase, total bilirubin, total protein, albumin, uric acid).	
Fasting Lipids include triglycerides, total cholesterol, HDL and LDL.	
3. Disease Assessment/Tumor Measurements: Re-staging imaging studies will be performed after every two cycles of treatment (1 cycle = 4 weeks) during the first five years of treatment and after study completion or withdrawal. Imaging studies should be performed during weeks 7 or 8. The same imaging studies performed at baseline (e.g., CT or MRI) should be performed throughout the study, when possible. Baseline chest CT or chest x-ray must be performed. If chest CT or chest x-ray is not part of the disease assessment, it must be repeated every 2 months. Bone x-ray(s)/scan to be performed if bone metastases are present.	
4. Adverse Events: Patients must be followed for adverse events from the first day of study treatment until at least 28 days after the last on-study treatment administration, or until all serious or study drug-related toxicities have resolved or are determined to be "chronic" or "stable," whichever is later. Serious adverse events should be monitored and reported as described in the protocol.	
5. Post-study survival status: Follow-up survival information will be collected for all patients by clinic visit or telephone contact approximately every 6 months for up to 2 years from the date of first dose of Everolimus. Patients will be followed until disease progression and/or death.	
6. Physical Examination/Hematology/Biochemistry/Fasting Lipids: Physical Examination/ Hematology/ Biochemistry/Fasting Lipids on Cycle 1 Day 1 is not required if performed within 7 days of Day 1 unless clinically indicated.	
7. Post Treatment/Withdrawal: This visit will take place 1 month after the last dose of study drug. Patients with ongoing study drug-related toxicities should be followed as dictated in footnote 4. These patients should be followed at the interval deemed appropriate by their study physician.	

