### 12.4.5 Duration of Overall Response/ Progression Free Survival

The duration of overall response is measured from the time measurement criteria are met for CR or PR (whichever status is recorded first) until the first date that recurrence or PD is objectively documented, taking as reference for PD the smallest measurements recorded since the treatment started.

Progression Free Survival will be calculated from the start of treatment until progressive disease or death. Patients who die before documented progression will be considered failures at their time of death. If the patient did not progress or die, the patient will be censored on the date of last follow-up.

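### Dropping patients who stop in cycle 1 for progression-related deterioration biases the two-month PFS rate upward, weakens the Stage 1 futility stop, and puts the 5% type I error at risk

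*Combined protocol and SAP*

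**What the plan says.** Section 14.0 defines the endpoint as a proportion: "the primary endpoint of this study will be the proportion of patients who are progression-free after two months on-study". The design is Simon's minimax two-stage, with 50% not promising and 70% promising, and error limits of 0.05 and 0.20. On Stage 1 it says "In Stage 1 of the trial, 23 evaluable patients will be accrued to the study". With 13 or more progression-free, "enrollment will be extended to accrue a total of 37 patients", and 24 or more progression-free is a positive result. It adds: "The probability of early stopping under the null hypothesis is 66" percent.

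The same section removes from the primary objective any patient who received no more than one cycle and was "discontinued from protocol treatment for either rapid clinical deterioration related to progression of disease or adverse events unrelated to Everolimus". These patients remain evaluable for toxicity.

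Section 12.4.5 reads differently: "Progression Free Survival will be calculated from the start of treatment until progressive disease or death". It counts death before documented progression as a failure and sets no minimum exposure.

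Footnote 3 to the Schedule of Events (Section 10.0) times the restaging scan: "Imaging studies should be performed during weeks 7 or 8". Disease assessment is also scheduled at the post-treatment/withdrawal visit, for which footnote 7 says "This visit will take place 1 month after the last dose of study drug".

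**The concern.** The exclusion depends on the outcome. A patient who stops in cycle 1 for deterioration that the rule itself attributes to progression is, in substance, not progression-free at two months. The scan comes in weeks 7 or 8, so for these patients the rule, not the scan, decides how they count. Removing them takes failures out of the denominator and no successes out of the numerator, so the rate rises whatever the drug does.

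Three results are affected:

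- **The reported two-month rate**, which is read against a fixed 50% benchmark with no control arm.
- **The Stage 1 futility stop**, because the 23 are explicitly evaluable patients and each removed failure is therefore replaced.
- **The type I error**, depending on whether removed patients are also replaced in reaching 37. The text does not say.

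No all-treated analysis of the primary endpoint is described that would show the effect. In addition, inevaluability is limited to the primary objective. Read literally, the same patients stay in the PFS used for the marker log-rank test in Section 14.0, so the two PFS results would rest on different patients. That last point is an inference, since no analysis set is named for the log-rank test.

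**Working it through.** **Inputs from Section 14.0.** n1 = 23, continue at 13 or more; N = 37, positive at 24 or more; p0 = 0.50; p1 = 0.70.

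**Step 1: reproduce the design.** With X1 the number progression-free in Stage 1 and X2 the number among the next 14:

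- Early stopping = P(Bin(23, p) ≤ 12)
- Positive result = Σ over x from 13 to 23 of P(X1 = x) · P(X2 ≥ 24 − x)

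At p = 0.50, early stopping is 0.661 and type I error 0.048. At p = 0.70, power is 0.801. The stated 66%, 0.05 limit and 80% are all reproduced.

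**Step 2: put in the exclusion.** Let e be the share of treated patients removed for progression-related deterioration. The documents give no value, so e is an assumption. All those removed are taken as failures, and the true all-treated rate as p = 0.50. The rate among evaluable patients is then q = p/(1 − e). For example, 0.50/0.90 = 0.556.

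**Step 3: recompute** under three readings of the final 37:

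- *Both stages*: removed patients are replaced throughout, so q applies to all 37.
- *Stage 1 only*: 23 evaluable patients at rate q, then 14 treated patients at rate p, none replaced.
- *Total accrual*: 23 evaluable in Stage 1 but 37 accrued in all, so each Stage 1 exclusion uses up one of the remaining 14 places. The number of exclusions is negative binomial. Excluded patients add no successes.

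| e | q | Early stopping | Type I: both stages | Type I: Stage 1 only | Type I: total accrual |
|---|---|---|---|---|---|
| 0 | 0.500 | 0.661 | 0.048 | 0.048 | 0.048 |
| 2.7% (about 1 in 37) | 0.514 | 0.611 | 0.068 | 0.060 | 0.0487 |
| 5% | 0.526 | 0.564 | 0.090 | 0.072 | 0.0490 |
| 10% | 0.556 | 0.451 | 0.162 | 0.108 | 0.0493 |
| 15% | 0.588 | 0.328 | 0.279 | 0.161 | 0.0494 |

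The early-stopping column is the same under all three readings, because it depends only on the 23 evaluable patients. With replacement in both stages, type I error passes 0.05 at e of about 0.3%. Under total accrual it cannot exceed P(Bin(37, 0.50) ≥ 24) = 0.0494.

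**Step 4: effect on the reported rate.** These counts are illustrative. With replacement, a reported 24/37 = 65% is 24/39 = 62% of treated patients if two were removed, and 24/41 = 59% if four were. Without replacement, two removals among 37 treated would report 24/35 = 69% where the all-treated rate is 24/37 = 65%. The rate is too high in each case.

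**The case against.** The strongest objection concerns type I error. The protocol speaks of accruing a total of 37, without the word evaluable, and success is an absolute count of 24. If 37 is total accrual, excluded patients cannot add to that count and type I error stays at or below 0.0494. This stands: inflation depends on replacement that the text does not state for the final 37. The text does not rule replacement out either, since Stage 1 is counted in evaluable patients and the 37 builds on it. The risk is real but conditional. The objection does not touch the Stage 1 stop or the upward bias in a rate reported among evaluable patients.

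Other points stand in part:

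- **The size is assumed.** The rule is narrow (at most one cycle, stopped, for a listed reason), and nothing in the documents supports a particular share. The 50% null is taken to apply to all treated patients. Section 14.0 bases it on a historical median of two to three months and does not say that early failures were left out.
- **The Stage 1 rule has a gap.** Twelve or more progressions on imaging means at most 11 progression-free, while continuing needs 13, so exactly 12 has no rule. The table uses stopping at 12 or fewer, which matches the stated 66%. Stopping only at 11 or fewer gives 50%, falling to 40%, 29% and 19% at 5%, 10% and 15% removed. The direction is the same.
- **Clinical deterioration is not RECIST progression.** Without imaging or death, such a patient is not strictly an event under Section 12.4.5 and might be censored. That calls for an explicit rule. Removing the patient is not a neutral substitute, because it raises the rate.
- **The unrelated-adverse-event reason** has no known direction. Nothing here rests on it.

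**Conclusion.** The concern holds. For the progression reason, the evaluable rate cannot be lower than the all-treated rate, provided those removed are failures, as the rule's own wording implies. The Stage 1 stop is weakened under every reading of the 37, from 66% to between 56% and 33% for assumed shares of 5% to 15%. Over the same range, type I error is 0.090 to 0.279 with replacement in both stages, 0.072 to 0.161 with replacement in Stage 1 only, and below 0.05 if 37 is total accrual. Confidence is high on direction. The magnitudes are conditional on the assumed share and on a 50% null for all treated patients. Because the rule governs the primary endpoint and the stop/go decision, it must be fixed.

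**What to change.** Revise Section 14.0 as follows:

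1. Apply the 13/23 and 24/37 cut-offs to consecutive patients who received at least one dose, and say that both the 23 and the 37 are treated patients. In the same edit, state that Stage 1 stops at 12 or fewer progression-free, which is the rule behind the stated 66%.
2. Count death, and cycle-1 deterioration attributed to progression, as not progression-free at two months. Say openly that the latter adds a clinical failure to an endpoint otherwise determined by RECIST, and cross-refer from Sections 12.1 and 12.4.5.
3. Classify patients who stop for unrelated adverse events by their status at the week 7–8 scan or at the withdrawal disease assessment.
4. Keep the present evaluable set, including the unrelated-adverse-event exclusion, as a sensitivity analysis only, listing each excluded patient and the reason.
5. If patients with no two-month status for other reasons, such as withdrawal, are also counted as not progression-free, say that this is conservative and differs from the censoring in Section 12.4.5, and show the result without it.

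The cost is a rewritten paragraph in Section 14.0 and short cross-references. No extra patients or procedures are needed, since disease assessment at withdrawal is already scheduled. The cut-offs keep their stated properties (type I error 0.048, power 0.80, early stopping 0.66). The price is a somewhat lower reported rate and some failures that rest on investigator judgement in an open-label trial. The listing and the sensitivity analysis make those visible.

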### 3.1 BACKGROUND AND RATIONALE

#### 3.2 Urothelial Cancer

In the United States, urothelial carcinoma (UC) of the bladder is the fourth most common malignancy in men and the ninth most common in women with an estimated 67,160 new cases (50,040 men and 17,120 women) and 13,750 deaths (9,630 men and 4,120 women) for the year 2007[1]. Although UC is a chemosensitive malignancy with response proportions of over 50% with conventional cytotoxic regimens, the response durations are short and the median survival of patients with metastatic disease is approximately 14 months [2]. Second-line trials with cytotoxic agents have generally yielded discouraging response rates (see table below) with a median progression-free survival between 2 to 3 months and a median survival in the range of 6 to 9 months[3-6]. Furthermore, many patients receive these agents as part of first-line therapy leaving few available options for patients with progressive or recurrent disease. There is no FDA-approved drug for this setting and no standard conventional chemotherapy agent(s) have demonstrated a survival benefit in patients with metastatic urothelial cancer that has progressed after first line platinum-based chemotherapy. This highlights the need for the development of

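### Section 14 lets a cycle-1 death judged unrelated to Everolimus drop out of the two-month PFS rate, although Section 12.4.5 counts every such death as a failure

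*Combined protocol and SAP*

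**What the plan says.** Section 12.4.5 measures PFS from the start of treatment to progression or death. On deaths it is explicit and makes no distinction by cause: "Patients who die before documented progression will be considered failures at their time of death".

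Section 14.0 makes the primary endpoint the proportion progression-free at two months. "A two-month progression free survival rate of 50% would be considered not promising", "while a 70% two-month PFS rate would be considered promising", and the "error rates have been set at 0.05 and 0.20, respectively". The design is Simon's minimax: continue if at least 13 of 23 are progression-free, and declare the drug effective if at least 24 of 37 are. Stage 1 is counted in evaluable patients: "In Stage 1 of the trial, 23 evaluable patients will be accrued to the study".

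A bold paragraph in the same section then defines who is inevaluable for this endpoint. These are patients who receive one cycle or less (one cycle is 4 weeks, Section 1.0) and stop protocol treatment for either of two reasons. The first is rapid clinical deterioration from progression. The second is "adverse events unrelated to Everolimus". This point concerns the second reason only. The paragraph says nothing about patients who die.

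**The concern.** Take a patient who has a fatal embolism in week 3. Under Section 12.4.5 the patient is a failure. Under Section 14, if the event is judged unrelated, the patient is in neither the numerator nor the denominator. If it is judged related, the patient stays in as a failure. One relatedness call therefore decides whether a known PFS failure counts. The trial is single-arm and open-label, and for a fatal event the call is made after that patient's outcome is known.

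The same applies to a living patient who stops early for an unrelated event and is then found to have progressed by two months.

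Because Stage 1 is filled with evaluable patients, a removed failure is replaced by someone else. The rate compared with the fixed 50% benchmark is then not the rate among treated patients. The final decision is a single count against 24 of 37, so one or two patients can settle it.

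**Working it through.** **Inputs from Section 14.0:** null rate 0.50; alternative 0.70; stage 1 n = 23, continue if at least 13; total N = 37, success if at least 24. The share q of treated patients who are PFS failures removed by the unrelated-event limb is not given. It is varied from 1% to 5% as an assumption. All 37 are taken to be evaluable patients.

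**Step 1: reproduce the design.** With true rate p among those counted:

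- Early stopping = P(Bin(23, p) ≤ 12).
- P(positive) = Σ over x = 13 to 23 of P(Bin(23, p) = x) × P(Bin(14, p) ≥ 24 − x).

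At p = 0.50 this gives early stopping 0.661 and type I error 0.0482. At p = 0.70 it gives power 0.801. These match the stated 66%, 0.05 (as a ceiling) and 80%. A search over two-stage designs returns the same minimax design.

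**Step 2: remove failures only.** If a share q of treated patients are failures and are dropped, the rate among the rest is p/(1 − q). For example, with p = 0.50 and q = 5%, 0.50/0.95 = 0.526. The rule of Step 1 at each such rate gives:

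| q (removed failures) | Rate tested | Type I error | Early stopping |
|---|---|---|---|
| 0 | 0.500 | 4.8% | 66.1% |
| 1% | 0.505 | 5.5% | 64.3% |
| 2% | 0.510 | 6.2% | 62.4% |
| 2.7% (1 in 37) | 0.514 | 6.8% | 61.1% |
| 3% | 0.516 | 7.0% | 60.5% |
| 5% | 0.526 | 9.0% | 56.4% |

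In counts, a just-positive 24/37 = 64.9% becomes 24/38 = 63.2% with one removed death restored as a failure, and 24/39 = 61.5% with two.

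**Step 3: allow a mix.** The limb also removes living patients. If a fraction f of those removed would have been progression-free at two months, the tested rate is (p − q·f)/(1 − q). With p = 0.50 and q now meaning all patients removed, set at 5%:

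| f | Rate tested | Type I error |
|---|---|---|
| 0 | 0.526 | 9.0% |
| 25% | 0.513 | 6.7% |
| 50% | 0.500 | 4.8% |
| 75% | 0.487 | 3.4% |

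The break-even is f = p: when half of those removed would have been progression-free, nothing changes under the null.

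**Step 4: are cycle-1 deaths plausible at all?** Section 3.2 cites "a median survival in the range of 6 to 9 months" in second-line cytotoxic trials. If survival were exponential with median m months, 28-day mortality would be 1 − 2^(−(28/30.44)/m). That is 10.1% for m = 6 and 6.8% for m = 9, or 3.7 and 2.5 deaths in 37. This shows only that some cycle-1 deaths are to be expected. It is not an estimate of q.

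**The case against.** **The sections can be read together.** Section 14 speaks of patients discontinued from treatment and never mentions death. Section 13.0 does not list death among the reasons treatment stops. One can therefore let 12.4.5 govern deaths and let the evaluability rule govern living patients who stop early. That reading is possible, but no section states it. A fatal adverse event ends treatment, and nothing exempts it from the rule, so the ambiguity on the primary endpoint remains.

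**The limb may not inflate anything.** A reader might infer that it raises the type I error as a whole. The documents do not support that. Step 3 shows that it can be neutral or conservative, depending on how the removed living patients fare. This stands, and it confines the inflation figures to removed failures.

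**The frequency is unknown.** A reader might take the 7% to 10% early mortality as the share removed. It is all-cause, rests on an exponential assumption, comes from other trials, and is not adjusted for this trial's entry criteria. Many such deaths would be from progression, which is the other limb. Fatal infections would be hard to call unrelated, since Section 11.0 describes Everolimus as predisposing to infection. This stands too.

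**Attribution is not unchecked.** Section 17.3.1 requires each serious event to reach the IRB within 5 calendar days, with its relationship to treatment and the principal investigator's signature. Section 16.3 describes a monitoring committee for Phase II trials. The call is thus recorded promptly and probably before any pooled result, so a reading of deliberate relabelling has no support. It is still made knowing that patient's outcome, and the documents describe no independent adjudication of relatedness.

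**Conclusion.** The inconsistency is real and concerns the primary endpoint. As written, Section 14 can drop a death that Section 12.4.5 counts as a failure, and an open-label causality judgement decides which happens.

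Its size rests on an assumption. If 1% to 5% of treated patients are removed failures and the true all-treated rate is 50%, type I error is about 5.5% to 9.0% against 4.8% for the design, and early stopping about 64% to 56% against 66%. One such patient in 37 is enough to pass the stated 0.05. The direction is certain for removed deaths and progressions only; the net effect of the limb depends on the mix of patients removed. The documents show neither that the limb as a whole biases the trial toward a positive result nor how often it would be used. It should be corrected because the correction is cheap and leaves the primary rate with one definition.

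**What to change.** Amend Section 14 in three respects:

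1. State that death from any cause, or progression, within two months counts as not progression-free in the primary rate, in line with Section 12.4.5 and whatever the attribution of any adverse event.
2. Classify living patients who stopped early from their two-month scan. For those without one, fix a single primary rule, so that the 13-of-23 and 24-of-37 decisions are defined. One option is to count them as not progression-free.
3. Report the evaluable-only rate as a sensitivity analysis.

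This can be done in the same edit as the progression limb of that sentence.

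The cost is a few sentences, one extra line of results and a slightly less favourable observed rate. A reader might infer that the change costs power. If the 50% and 70% rates are defined with all deaths counted, the design keeps its 4.8% type I error and 80% power. Counting unscanned living patients as not progression-free is conservative, and would lower the chance of a positive result if some of them were in fact progression-free. That is a reason to obtain the scheduled two-month scan in patients who stop early.
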